It is able to track progress and outcomes, and is helpful to the support process when used interactively with the family. The SCORE-15 has 15 Likert scale items and six separate indicators, three of them qualitative. It is appropriate for use with individuals, couples and full families when relationships within the family is relevant to the support being given. It is relevant when working systemically with an individual, in relation to their significant relationships, when working with members of more than one family (multi-family work), and in sessions involving family member(s) and professionals. It records perceptions of the family from each member over the age of 11 years. There is also a version for children aged 8 to 11 years which will be used in the pilot.⁷⁵

In the original development of the measure, extensive consultations with therapists, service users and researchers were undertaken to obtain simple and unambiguous items that would be meaningful to families from a wide variety of cultural, ethnic and socioeconomic backgrounds.⁷⁶

It has been shown to be reliable and valid both as an indicator of the quality of interactions within the family and as a measure of therapeutic progress early in family and couples therapy.⁷⁷ The measure had been found to have good internal reliability with alpha coefficients for overall scales and subscales above 0.7. Cronbach alphas for the SCORE-15 and SCORE-28 totals were 0.90 and 0.93, respectively. The SCORE-15 has also been found to have good test-retest reliability and good criterion validity, discriminating between clinical and non-clinical cases.⁷⁸

⁷⁴ Stratton, P, Bland, J., Janes, E & Lask, J. (2010) Developing a practicable outcome measure for systemic family therapy: The SCORE. *Journal of Family Therapy*. 32, 232-258 <https://doi.org/10.1111/j.1467-6427.2010.00507.x>

⁷⁵ Jewell, T., Carr, A., Stratton, P., Lask, J., & Eisler, I. (2013). Development of a Children's Version of the SCORE Index of Family Function and Change. *Family Process*, 52 (4), 673-684.

⁷⁶ https://www.corc.uk.net/media/1249/score_userguide.pdf

⁷⁷ Stratton, P., Lask, J., Bland, J., Nowotny, E., Evans, C., Singh, R., Janes, E. and Peppiatt, A. (2014), Validation of the SCORE-15 index. *J. Fam. Ther.*, 36: 3-19. <https://doi.org/10.1111/1467-6427.12022>

⁷⁸ Hamilton, E., Carr, A., Cahill, P., Cassells, C., & Hartnett, D. (2015). Psychometric Properties and Responsiveness to Change of 15- and 28-Item Versions of the SCORE: A Family Assessment Questionnaire. *Family Process*, 54 (3), 454-463.

It can be administered in less than 10 minutes, is free to use, and has a variety of clinical and non-clinical uses as well as being usable for research and audit. SCORE-15 has been translated into a range of other languages by practitioners.⁷⁹ It was also used successfully in the Foundations feasibility studies in Rotherham and Greenwich.

Consultation and Relational Empathy (CARE)

The Consultation and Relational Empathy (CARE) Measure is a person-centred measure that looks at empathy in the context of the relationship between a practitioner and a beneficiary.⁸⁰

The Consultation and Relational Empathy (CARE) Measure is a patient-rated experience measure of the interpersonal quality of healthcare encounters. Empathic person-centred care is central to high quality support from practitioners. Research has linked empathic care to higher levels of patient satisfaction, enablement and improved health outcomes.⁸¹

Originally developed and rigorously tested for use by doctors, it is now widely used in GP settings, and it has since been successfully used by other professionals.⁸² It has been found to have high face and construct validity, high internal consistency (Cronbach's alpha coefficient = 0.97) and acceptable inter-rater reliability (G = 0.6 with 60 patients ratings per nurse). In addition, factor analysis has found that the CARE Measure items load highly onto a single factor and scores were not affected by patients' age, gender, self-perceived overall health, living arrangements, employment status or language spoken at home.⁸³

Its ten items ask beneficiaries' perception of the practitioner's 'relational empathy', defined as the practitioner's ability to:

- understand the beneficiary's situation, perspective and feelings (and their attached meanings);
- communicate that understanding and check its accuracy, and
- act on that understanding with the beneficiary in a helpful (therapeutic) way.

⁷⁹ <https://www.aft.org.uk/page/scoretranslations>

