Table 4: Secondary outcome for families 1

| | |
|----------|---|
| Variable | Family functioning |
| Measure | SCORE-15 Index of Family Functioning and Change ⁶⁴ |

⁶¹ Bradley, J., Murphy, S., Fugard, A. J., Nolas, S. M., & Law, D. (2013). What kind of goals do children and young people set for themselves in therapy? Developing a goals framework using CORC data. *Child and Family Clinical Psychology Review*, 1(1), 8-18.; Law,D.,& Bradley,J.(2015).Goals and Goal Based Outcomes(GBOs): Some Useful Information.(3rd ed.) London: CAMHS Press.

⁶² Mok, W. C., Vainieri, I., & Jacob, J. (2024). Exploring goal taxonomies using the goal-based outcome tool in children and young people's mental health settings. *Counselling and Psychotherapy Research*, 24(2), 472-490.

⁶³ Banwell, E., Salhi, L., Hanley, T., & Facey-Campbell, N. (2023). The use of goal-based outcome measures in digital therapy with adults: What goals are set, and are they achieved?. *Counselling and Psychotherapy Research*, 23(3), 770-780.

| | |
|------------|---|
| Sample | Families – Score-15 is administered at an individual level with the child/young person referred to the keyworkers and at least one parent/carer. Scores are then combined into a composite score for the family. |
| Time point | Baseline: within the assessment period of the first six weeks of the keyworker working with a family. Midline: at a review point when working with the family. Typically this is between two to five months of working with the family. Endline: At closure when the keyworker stops working with a family. |

Table 5: Secondary outcome for families 2

| | |
|------------|--|
| Variable | Therapeutic alliance – relationship between the family and keyworker |
| Measure | The Consultation and Relational Empathy (CARE) measure ⁶⁵ |
| Sample | Children/young people and parents/carers. The CARE measure will be administered at an individual level, for parents/carers and young people ages 11 and older, and a version for children aged 8-11. Scores will not be combined but reported separately Families - 10 questions on the relationship between the family and the keyworker. |
| Time point | Baseline: within the assessment period of the first six weeks of the keyworker working with a family. Midline: at a review point when working with the family. Typically this is between two to five months of working with the family. Endline: At closure when the keyworker stops working with a family. |

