As a minimum, at least one parent/carer and the child will need to complete the questionnaire at least two timepoints: baseline and at mid or endline. Ideally, all family members (including other carers and children) working with the keyworker will also complete the questionnaire. Keyworkers judgement will be used when deciding whether the child or young person is capable of completing the questionnaire. Versions of each measure have been developed for children aged 8 and over.

The questionnaire will be available online using a link provided to keyworkers, as well as paper versions for practitioners or administrators to upload. All families in the trial will be provided with an easy-read sheet on the outcome measures as part of their privacy notices and online consent form within the outcome questionnaire.

Training, guidance and support will be provided to keyworkers and those supporting data collection in the local authorities. Refresher training and ongoing support will be provided by Coram and the local systemic practitioner. The Family Outcome Questionnaire is included in Annex B.

Supporting Families Data collection

Data for two secondary outcome measures (whether a family has been stepped-up into statutory support and whether a family has been closed with positive progress as part of the Supporting Families Programme) will be collected indirectly from families through data local authorities collect as part of their early help data collection as part of the Supporting Families Programme. Families will consent to this data being provided via their consent forms and local authorities will provide this data as part of the Data Sharing Agreement agreed with each local authority.

To minimise the burden on families and keyworkers and to maximise the analysis that can be undertaken, local authorities will also be asked to provide additional data on the families already collect this data as part of their case management systems provided via DfE's early help dataset.

This additional data is currently being collected at two time points by local authorities:

- 1) In the assessment period when the keyworker first starts to work with a family usually within the first six weeks of working with a family.
- 2) At closure when the keyworker stops working with a family.

Baseline data will include demographic information on:

- Child Date of Birth

- Parent/carers Date of Birth
- Relationship of the parent/carer to the child
- Sex of the child

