7. **Being positive** (*having a positive approach and a positive attitude; being honest but not negative about your problems*)

8. **Explaining things clearly** (*fully answering your questions, explaining clearly, giving you adequate information; not being vague*)
9. **Helping you to take control** (*exploring with you about what you can do to improve your health yourself; encouraging rather than 'lecturing' you*)
10. **Making a plan of action with you** (*discussing the options, involving you in decisions as much as you want to be involved; not ignoring your views*)

Thank you for completing this questionnaire, it is an important part of the pilot.

For further information on how this information will be used, please see the **Date Privacy Notice**: <https://www.coram.org.uk/wp-content/uploads/2024/11/Systemic-Practice-DPN-parents-carers-and-children-FINAL.pdf>

Systemic Practice Pilot Family Outcomes Questionnaire

CHILD (8-17 years old) QUESTIONNAIRE – PAPER VERSION

This is a paper copy of the Family Outcomes Questionnaire for **child (aged 8 and over)** family members as part of the Systemic Practice Pilot Study. We are using this questionnaire to support the evaluation of the pilot.

Please also take a paper copy of the privacy notice to give to parent/carers and children **before** they consent to completing the questionnaire: <https://www.coram.org.uk/wp-content/uploads/2024/11/Systemic-Practice-DPN-parents-carers-and-children-FINAL.pdf>

Information collected on this paper version should be uploaded via the link: <https://www.smartsurvey.co.uk/s/FamilyOutcomeQuestionnaire/>

Administrative information for the Keyworker to complete

1. **Please write the local authority ID number for the child completing the questionnaire. The ID will be the one you use in your service for the child.**

Providing this is very important as it will allow us to use the questionnaire data in the pilot.

2. **Child ID**

Has this child completed the questionnaire before?

- No, this is their first time completing the questionnaire
- Yes, they have completed the questionnaire before, and today they are completing it as part of a review of their progress
- Yes, they have completed the questionnaire before, and they are completing it as part of ending our support (case closure)

3. Please state roughly how long you have worked with the child. If the child have been re-referred, please state how long you have been working with them since the rereferral.

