- Less than a week 9 to 12 weeks
- 1 to 2 weeks 3 to 6 months
- 3 to 4 weeks 7 to 12 months
- 5 to 8 weeks Over 12 months

Introduction

Thank you for agreeing to fill in this questionnaire.

The questions will cover:

- **Your family** –15 questions about how you see your family at the moment.
- **Your goals** –goals (up to three) you want to achieve for your family through this service. It also asks about your progress towards these goals.
- **Your keyworker** –10 questions about your relationship with your keyworker.

If you have any questions when completing the questionnaire **please ask your keyworker and they will be able to help you.**

Section 1: Your Family

In this section we would like you to tell us about how you see your family at the moment. **So we are asking for your view of your family.** When people say 'your family' they often mean the people who live in your house. **But we want you to choose who you want to count as the family you are going to describe.**

There are 15 short questions. Please tick whether the statement describes your family very well through to not well at all. For example, if a statement was "We are always

fighting each other" and you felt this was not especially true of your family, you would tick the box that says "Describes us: not well".

Very Well / Well/ / Partly / Not very well / Not at all

X

Do not think for too long about any question, but do try to tick one of the boxes for each question.

For each line, would you say **this describes our family**: Very well / Well / Partly / Not very well / Not at all / Do not want to answer

1. In my family we talk to each other about things which matter to us
2. People often don't tell each other the truth in my family
3. Each of us gets listened to in our family
4. It feels risky to disagree in our family
5. We find it hard to deal with everyday problems
6. We trust each other
7. It feels miserable in our family
8. When people in my family get angry they ignore each other on purpose
9. We seem to go from one crisis to another in my family
10. When one of us is upset they get looked after within the family
11. Things always seem to go wrong for my family
12. People in the family are nasty to each other
13. People in my family interfere too much in each other's lives
14. In my family we blame each other when things go wrong
15. We are good at finding new ways to deal with things that are difficult

Section 2: Your Goals

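### The only child paper form in Annex B gives ages 8-11 the adult SCORE-15 items and gives teenagers the child CARE and child GBO layout, contrary to the age bands in the protocol text

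*Protocol*

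**What the plan says.** **SCORE-15.** Under Secondary outcome measures (families), the protocol describes the standard instrument thus: "It records perceptions of the family from each member over the age of 11 years". For younger children it adds: "There is also a version for children aged 8 to 11 years which will be used in the pilot". Table 4 has the measure completed individually by the referred child and at least one parent or carer, and then states: "Scores are then combined into a composite score for the family".

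**CARE.** Table 5 sets out two versions: "for parents/carers and young people ages 11 and older, and a version for children aged 8-11". CARE scores are reported separately and not combined.

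**GBO (primary outcome).** Table 3 gives the adult version to adults and to young people over 12, and a child-friendly version to ages 8 to 12.

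**General statement.** The Data collection section says: "Versions of each measure have been developed for children aged 8 and over". It refers the reader to Annex B for the questionnaire.

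**Annex B.** Two forms are printed: one for adult family members, and one headed "CHILD (8-17 years old) QUESTIONNAIRE – PAPER VERSION". There is no separate form for ages 8-11 and none for teenagers.

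**The concern.** The text describes age-specific versions of three measures, each with its own cut-off. The annex prints one child form that applies none of those cut-offs. If the printed form is what families receive, children aged 8-11 answer a version of SCORE-15 below its stated age range, and those answers feed the composite for family functioning, the first secondary outcome. The reliability and validity evidence the protocol cites for SCORE-15 cannot be assumed to carry over to those respondents. For CARE, results for older children would be reported under the name of a version they did not receive.

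A pilot has a further stake. The section on feasibility for a full-scale trial lists the appropriateness of measures among its outputs. That cannot be judged for the children's SCORE-15 if it was never given.

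**Working it through.** No power or sample size figure is in question. The check compares the two printed forms and then sets the printed child form against the stated age bands.

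**1. SCORE-15 items, adult form against child form.** All 15 of 15 items are identical, including the more abstract ones such as "People in my family interfere too much in each other's lives". The introduction and response options are also the same. The wording of the children's SCORE-15 is not reproduced anywhere in the protocol. That the promised version is absent is therefore inferred: the text describes a separate version, and the form shows no difference from the adult one.

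**2. Version stated against version printed on the child form.**

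| Measure | Age | Stated in text | Printed on the 8-17 form |
|---|---|---|---|
| SCORE-15 | 8-11 | children's version | standard version (mismatch) |
| SCORE-15 | 12-17 | standard version | standard version (agrees) |
| CARE | 8-10 | child version | child version (agrees) |
| CARE | 11 | in both Table 5 bands | child version (ambiguous) |
| CARE | 12-17 | standard version | child version (mismatch) |
| GBO | 8-12 | child-friendly version | child layout, 0-10 (agrees) |
| GBO | over 12 | adult version | child layout, 0-10; adult form prints 1-10 (mismatch) |

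**3. How many children.** Table 2 expects 294 children and 560 families in the analysed sample. It gives no ages, so the true counts cannot be derived. As an illustration only, assume ages spread evenly over the ten single years 8 to 17:

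- SCORE-15, ages 8-11: 4/10 × 294 = 117.6, about 118 children. If each is in a different family, 118/560 = 21% of families, which is the upper limit under this assumption.
- CARE, ages 12-17: 6/10 × 294 = 176.4, about 176 children. If age 11 is read as belonging to the standard version, 7/10 × 294 = 205.8, about 206.
- GBO, ages 13-17: 5/10 × 294 = 147 children.

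**4. Could the online form differ?** The questionnaire is offered online as well as on paper, and the online form is not shown. The child paper form asks for an ID, prior completion and length of support, but not age, and both paper forms are uploaded through the same link. Nothing describes routing by age, but nothing rules it out. If routing exists, Annex B does not show what is used and still needs correcting.

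**The case against.** The strongest reply is that this is a discrepancy between text and annex with modest consequences. Much of that stands, and it rules out several stronger readings that a reader might be tempted by.

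- *All child scores come from the wrong version.* Not so. Those aged 12-17 receive the stated SCORE-15, and those aged 8-10 receive the stated CARE. Counting all 294 children as affected on SCORE-15 would overstate the problem.
- *The affected scores are lost once collected.* Not so. SCORE-15 is administered individually, the child form carries its own Child ID, and child date of birth is among the data requested from local authorities. Scores from ages 8-11 can be identified at any time before or after the composite is formed.
- *The composite is shifted by a known amount.* The documents contain nothing from which to estimate the difference between versions. Table 4 says only that scores are combined, not how.
- *The comparison between arms is biased.* No arm-specific form appears, so the documents show no differential error.

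For CARE, the child version keeps the same ten topics and the same poor-to-excellent ratings with shorter explanations, and scores are not pooled. The harm there is mainly one of labelling.

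The reply does not dispose of the SCORE-15 point. Followed as printed, Annex B gives 8-11 year olds an instrument outside its own stated age range and passes the result into a named outcome.

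**Conclusion.** The contradiction is confirmed. On the printed paper form, ages 8-11 answer the standard SCORE-15 in place of the promised children's version, and ages 12-17 answer the child CARE in place of the standard one. Age 11 is unassigned for CARE because it falls in both bands. The GBO layout for those over 12 also departs from Table 3, and it uses a different response range from the adult form. The consequence is doubtful measurement validity and added noise in the family composite, together with mislabelled CARE results.

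The size is uncertain. The counts of about 118 (SCORE-15) and 176 (CARE) rest wholly on an assumed even age spread. The conclusion also assumes that the online form matches the paper one and that the children's SCORE-15 differs from the standard items. The point merits correction because the remedy is cheap; it does not threaten the trial's main comparison on the evidence given.

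**What to change.** **Documents.** Reconcile Tables 3, 4 and 5, the SCORE-15 description and the Data collection section with Annex B. State non-overlapping age bands for each measure, assign age 11 to one CARE version, and say whether the online form routes by age.

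**New respondents.** Issue the promised 8-11 SCORE-15 to children in that band and the standard CARE to those in the older band. Resolve the GBO layout in line with whatever Table 3 finally states. Keep each respondent on the version used at baseline, so that change scores do not mix versions, and record the version received.

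**Data already collected on the single form.** Use Child ID and date of birth to identify ages 8-11. Run a sensitivity analysis of SCORE-15 without their standard-version scores, or at respondent level with a term for version or age band. Label CARE results for ages 12-17 as child-version.

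**Cost.** One additional form, drawn from versions the protocol says exist, and an age split in the analysis. In the sensitivity analysis that omits the 8-11 scores, some families will lose the child's view that Table 4 asks for, so it should be reported beside the main result and not replace it.

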The Professional Wellbeing Self-assessment tool was developed for the DfE by [name] and [name] with Research in Practice. It looks at professional wellbeing in a social care context and assesses holistic professional wellbeing by looking at professional's own perspective, self-management, meaningfulness, self-care, practice competency, and professional development. While the tool has not been used as an outcome measure in a research study, it has been piloted with a wide range of social work professionals with a mix of culture, age, gender, social work experience, fields of practice, and work environment.

The Social Work Organisational Resilience Diagnostic (SWORD) Tool was developed by Research in Practice and [name], University of Bedfordshire, and [name], Birkbeck University of London, was developed to improve organisational resilience in child and family social work. It is used as a diagnostic tool to explore respondents' experiences of wellbeing and resilience within five domains and has been used by several local authorities for a number of years. As with the Professional Wellbeing Self-Assessment Tool, SWORD tool has not been created for, or used in, a

⁸⁴ <https://caremeasure.stir.ac.uk/CARE%20other%20languages.htm>

⁸⁵ https://img1.wsimg.com/blobby/go/dfc1e1a0-a1db-4456-9391-18746725179b/downloads/ProQOL_5_English.pdf?ver=1657301051771

⁸⁶ <https://novopsych.com.au/assessments/clinician-self-assessment/the-professional-quality-of-life-scale-5-proqol/>

⁸⁷ Burridge, H., Nolan, J., & Stanford, M. (2023) Piloting the implementation of systemic training and feedback tools in Rotherham's Early Help & Family Engagement Service: Evaluation report. <https://www.eif.org.uk/files/pdf/piloting-implementation-systemic-training-feedback-tools-rotherham-early-help-family-engagement.pdf>

⁸⁸ https://practice-supervisors.rip.org.uk/wp-content/uploads/2024/05/PT-The-Professional-Wellbeing-Self-assessment-Tool_05.24FINAL.pdf

⁸⁹ <https://sword.researchinpractice.org.uk/about/>

research study to assess outcomes. As a result, adaptations were made to develop a bespoke set of questions to assess professional wellbeing in the context of the pilot study.

Adapted measure for Practice quality

A review of outcome measures assessing the quality of keyworker practice generally, and of systemic practice specifically, was undertaken as part of this project.

Unfortunately, no validated measure of either was identified. As a result, a set of questions were created to assess systemic practice quality based on the Systemic Therapy Inventory of Change (STIC), and the Systemic Practice Competency Scale (SPCS).

The Systemic Therapy Inventory of Change (STIC) is a multisystemic and multidimensional feedback system that provides therapists feedback about systemic domains of client change in individual, couple, and family therapy over time.

The Systemic Practice Competency Scale (SPCS) provides a structure for the assessment of Systemic Family Practice (SFP) skills to evaluate family therapy sessions as well as training and supervision. It covers 12 areas of systemic family practice: Interpersonal Effectiveness and Development of Therapeutic Alliance; Convening and managing the session; Collaboration; Conveying a Systemic View; Conceptual Integration; Use of Questioning; Feedback; Intervening in Process; Working with Power and difference; Exploring and managing emotions in sessions; Use of change techniques; and incorporating the outside World.

Data collection

Family Outcome Questionnaire

Data for the primary outcome measure (the Goal Based Outcome) and the first two secondary outcome measures (SCORE-15 and CARE measure) will be collected directly from families via an online Family Outcome Questionnaire administered by their keyworker in control and intervention local authorities. All families who are referred to keyworker teams for family support or early help within the timeframe of the pilot will be asked to complete the questionnaire by their keyworker. The questionnaire will form part of the standard assessment, review and closure process with families that keyworkers go through. Families and they will be supported to complete the questionnaire by their keyworker.

Baseline scores will be collected in the assessment period (first six weeks) when the keyworker starts working with a family. Midline scores (at least one) will be collected at a review point. Typically this is between two to five months of working with the family. Endline scores will be collected at closure when the keyworker stops working with a

family, or when the trial ends. Keyworkers will need to work with a family for a minimum of 10 weeks to be included in the trial analysis.

As a minimum, at least one parent/carer and the child will need to complete the questionnaire at least two timepoints: baseline and at mid or endline. Ideally, all family members (including other carers and children) working with the keyworker will also complete the questionnaire. Keyworkers judgement will be used when deciding whether the child or young person is capable of completing the questionnaire. Versions of each measure have been developed for children aged 8 and over.

The questionnaire will be available online using a link provided to keyworkers, as well as paper versions for practitioners or administrators to upload. All families in the trial will be provided with an easy-read sheet on the outcome measures as part of their privacy notices and online consent form within the outcome questionnaire.

Training, guidance and support will be provided to keyworkers and those supporting data collection in the local authorities. Refresher training and ongoing support will be provided by Coram and the local systemic practitioner. The Family Outcome Questionnaire is included in Annex B.

Supporting Families Data collection

Data for two secondary outcome measures (whether a family has been stepped-up into statutory support and whether a family has been closed with positive progress as part of the Supporting Families Programme) will be collected indirectly from families through data local authorities collect as part of their early help data collection as part of the Supporting Families Programme. Families will consent to this data being provided via their consent forms and local authorities will provide this data as part of the Data Sharing Agreement agreed with each local authority.

To minimise the burden on families and keyworkers and to maximise the analysis that can be undertaken, local authorities will also be asked to provide additional data on the families already collect this data as part of their case management systems provided via DfE's early help dataset.

This additional data is currently being collected at two time points by local authorities:

- 1) In the assessment period when the keyworker first starts to work with a family usually within the first six weeks of working with a family.
- 2) At closure when the keyworker stops working with a family.

Baseline data will include demographic information on:

- Child Date of Birth

- Parent/carers Date of Birth
- Relationship of the parent/carer to the child
- Sex of the child
- Sex of the parent/carers
- Ethnicity of the child
- Ethnicity of the parent/carers
- Whether the child has a Special Educational Needs (a SEN statement or Education Health and Care Plan)
- Whether the parent/carers have a disability
- The work status of the parent/carers
- Whether the child has English is an Additional Language
- Whether the parent/carers has English is an Additional Language
- The work status of the parent/carers
- Whether the child is eligible for Free School Meals.

Assessment data will also include information collected as part of DfE's early help dataset:

- Family ID
- Date assessment started
- Whether the case is a re-referral
- Whether the case is eligible for the Supporting Families Programme
- Family Need identified from items with the Supporting Families Outcome Framework⁹⁰

Closure data will include information collected as part of DfE's early help dataset:

- Family ID
- Reasons for closure
- Outcome at closure using items with the Supporting Families Outcome Framework⁹¹

Keyworker outcome measures

Data for the final two outcome measure (changes in professional wellbeing and changes in systemic practice) will be collected from all keyworkers in the study local authorities via an online survey emailed to them at the start of the trial and at the end of the study.

⁹⁰

https://assets.publishing.service.gov.uk/media/62471c2be90e075f08be4248/Annex_A_National_Supporting_Families_Outcome_Framework.pdf

⁹¹

https://assets.publishing.service.gov.uk/media/62471c2be90e075f08be4248/Annex_A_National_Supporting_Families_Outcome_Framework.pdf

Keyworkers in the intervention group will also be asked questions on these measures in a post-training survey.

Compliance and fidelity

Steps will be taken to monitor compliance and identify risks to contamination. The local authority level randomisation design has the advantage of making risks to contamination low as the model to embed systemic practice will only be implemented in intervention local authorities. In addition, local authorities in the trial are not geographical neighbours, meaning it is unlikely that families will move from one to another.

Eligibility for the pilot study also has the advantage of being determined by eligibility for support by keyworkers meaning that all families supported by a keyworker will be eligible to be included within the trial, if they consent to take part when completing the Family Outcomes Questionnaire. For families that do not consent to take part in the trial, we will request aggregate level anonymous data about these families from local authority case management administrative data. This will allow us to compare the characteristics of those who do and do not consent to the trial. This will include potential biases across characteristics such as type of need at referral, whether they are being re-referred as well as demographic characteristics such as, sex, race and ethnicity, and disability.

Coram was responsible for randomisation and undertook internal quality assurance checks to minimise any biases.

Coram will also explore the influence of trial arm allocation compliance using Complier Average Causal Effect Analysis (meaning whether families or keyworkers in the intervention arm receive the intervention), by including intervention receipt in an instrumental variable analysis. Keyworkers in the intervention arm that attend at least 80% percent (four out of five days) of the initial five-day systemic practice training for all keyworkers will be deemed compliant. This threshold of 80% was recommended by IFT based on their extensive experience of keyworkers being able to use and embed systemic training in their practice. IFT and the local authorities will record attendance of keyworker training which will be included in the administrative data collected.

Quality assurance of the Family Outcome Questionnaire data will be undertaken frequently, and any missing, anomalous or any potential biases in the data will be queried with the respective local authority. If any consistent issues are identified, additional guidance and targeted training for keyworkers and additional guidance within the questionnaire for families will be provided to help ensure compliance.

Implementation fidelity will be measured according to the core components of the systemic practice pilot. This is set out in the table below.

Table 10: Implementation fidelity measures for intervention local authorities

| Component of fidelity | Measure | Source |
|--------------------------------------|---|---|
| Training in systemic practice | 
 Leaders introductory day attended by the majority of early help senior staff. At least 90% of keyworkers attend at least 3 out of the 5 days of systemic training. At least 80% of keyworkers attend at least 4 out of the 5 days of systemic training. At least 60% of keyworkers attend all 5 days of systemic training. At least 50% of the 10-20% of keyworkers chosen as 'systemic champions' complete the 15 days of Foundation level training. | Data collected from IFT on attendance to training |
| Systemic practitioner | 
 A systemic practitioner trained to level two in systemic practice is employed for at least 12 out of the 15 months of the trial. Systemic reflective practice sessions held at least monthly for at least 12 out of the 15 months of the trial with at least 60% of keyworkers attending each session across teams. | Data collected from local authorities on hiring a practitioner and number of reflective practice sessions |
| Virtual Practice Hub | 
 At least 75% of keyworkers who attend IFT training access the virtual practice hub for one or more of the following types of support: i) training material from the 5 day course ii) additional training material and guidance not part of the 5 day course iii) Q&A and networking forms. | Data collected from IFT |

Fidelity will also be explored in the implementation and process evaluation. This will include interviews and focus groups with keyworkers, systemic practitioners and senior staff and observations of training, group reflective practice sessions, team meetings, and (if feasible) keyworker sessions with families. As well as Participatory Action Research (PAR) by embedded Systemic Practitioners and interviews with parent/carers and (if feasible) children and young people. They will be used to explore whether systemic practice was embedded in keyworker teams and whether systemic approaches were used with families in the intervention group.

These actions will help monitor fidelity and compliance as well as identify risks to contamination.

Analysis

A final Statistical Analysis Plan will be produced prior to any analysis detailing the analysis strategy in full.

Analysis will include a baseline description of the trial participants using baseline outcomes data and additional data provided by local authorities (see data collection above) and additional monitoring data from local authorities and IFT on fidelity as set out above. Descriptive statistics (means and standard deviations for continuous variables, percentages and counts for categorical variables) for each variable will be set out.

Outcomes analysis for the pilot study will include all randomised participants who provide outcome data across the pilot. Reporting will include participant flow throughout the trial, including completion rates of outcomes in a CONSORT diagram.

All outcomes will be analysed on an **intention-to-treat** basis meaning that all participants will be analysed according to the trial arm to which they were assigned, as opposed to whether the intervention was received.

We will calculate and report descriptive statistics, including the characteristics of the intervention and control groups on each key variable collected. We will carry out balance checks to report on how balanced the characteristics of respondents are across treatment and control groups. These characteristics will include the child/young person and parent/carers sex, age, ethnicity, English as an additional language, in addition to the child SEND status, child social care status, parent/carer disability, and parent/carer employment status.

Using this data, balance checks will be carried out to report on how balanced the characteristics of respondents are across treatment and control arms. For continuous variables (e.g. age), test balance will be undertaken using two sample t-tests with unequal variances. Balance in proportions (e.g. sex, ethnicity) will be tested using a chi-square test.

If any characteristics are significantly unbalanced between trial arms, these will be adjusted in the outcomes analysis. Analysis will report on full baseline characteristics of the sample including baseline outcome scores, the characteristics of those lost to follow-up, and the characteristics of the analysable sample. This will include the extent and pattern of missing data and explore this using regression modelling if required.

Missing data will be assessed to explore whether the data is:

- 1) *missing completely at random* (data is randomly distributed across the variable and unrelated to other variables),
